7.2. SAFETY ASSESSMENT

Any clinical manifestations, severity, time of occurrence, duration, treatment methods, and prognosis must be recorded in the participant's eCRF. The following safety parameters will be evaluated:

- Frequency and intensity of adverse events;
- Frequency and intensity of unexpected adverse events;
- Frequency and intensity of serious adverse events;
- Adverse events related to the experimental drug;
- Abnormal laboratory test values;

•

- Routine blood work (WBC count, RBC count, Hemoglobin, Platelet count, Neutrophil count, Lymphocyte count), ESR, IL-6, C-reactive protein, Liver function (AST/TGO, ALT/TGP, GGT, BT, ALP/FA), renal function (GFR, serum creatinine), coagulation function (APTT, TAP/PT, TT, FIB), blood lactate, cardiac enzymes and markers, procalcitonin, T lymphocyte subsets;
- Vital signs (body temperature, heart rate, respiration, blood pressure);
- Pregnancy test for women of childbearing age (blood);
- ECG.

Clinical safety will be assessed through spontaneous participant reports or direct observation by the Principal Investigator or his/her team on a daily basis, or by asking participants about adverse events on a non-induced basis. Participants will be screened with blood tests, imaging tests, respiratory tract tests, and vital signs, as listed in Table 39, as indicated, but not limited to these items.

7.3. VISIT SCHEDULE

The research center is responsible for defining the strategies for recruitment and initial screening of research participants, knowing that the screening process can be suspended at any time if exclusions are identified by the study team.

VISIT 1: INTIAL (D-1)

Patients with moderate to severe symptoms for COVID-19, hospitalized or with indication for hospitalization, aged over 18 years, will be invited to participate in the study. If the volunteer accepts to be a participant, he (she) and his (her) companion, if applicable, will be informed of the study procedures, including laboratory tests in the screening period, the criteria for inclusion and exclusion from the study, as well as his (her) rights and duties. Only after signing the informed consent form, the patient will be included in the study and the eligibility criteria can be explored after the anamnesis, laboratory tests, nasopharyngeal and oropharyngeal swab specimen collection for RT-

PCR testing, and imaging tests. **Confirmation of study participant eligibility will** be assessed once all screening data are available.

The following procedures will be performed in visit V1:

- Invitation to volunteer;
- Consent process and signing of the TCLE;
- Verification of inclusion and exclusion criteria;
- Demographic data collection;
- Anamnesis;
- Collection of medical history data;
- Vital signs monitoring;
- Collect blood and respiratory samples (nasal and oropharyngeal swabs) for screening tests;

- Collecting blood for a pregnancy test (women of childbearing age).
- Eligibility assessment and confirmation with the Principal Investigator.

VISIT 2: RANDOMIZATION (D0)

. After confirmation of eligibility for the study by meeting the inclusion and exclusion criteria and performing the screening procedures, eligible individuals will be randomized to the experimental or control group and then transferred to Santa Casa de Misericórdia de Campos for hospitalization in a ward/apartment, and will follow the Treatment Protocol for COVID-19 - 2nd Version (July 02, 2020) of Santa Casa de Misericórdia de Campos.

The following procedures will be performed in visit V2:

- Validation of eligibility by the Principal Investigator;
- Randomization of research participants;
- Admission or transfer of the participant to the apartment or infirmary of Santa Casa de Misericórdia de Campos;
- Dispensing of the experimental drug;
- Accounting for the experimental drug.

VISIT 3-16: PROCEDURE (D1-D14)

The treatment period will start on D1 according to randomization.

The treatment will last up to 14 days, and may be stopped early in case of treatment success (2 consecutive negative RT-PCR tests), participant dropout, or at the Principal Investigator's option, if deemed necessary for the safety of the participant.

For the **Early Termination (ETA)** of treatment, participants should follow the routine from visit 17: End of Treatment (D15), in advance.

The Principal Investigator for the study will be available to answer any questions.

The experimental drug should be administered daily at 8 pm to minimize the risk of falling, since in preliminary studies, it was observed that vertigo (incidence ≥5%) appears to be an AE likely related to FNC. However, no restrictions on meals.

The following procedures will be performed in the V3-16 visits:

- Administration AZVUDINE or PLACEBO daily, at the same time at 8pm, to minimize the risk of falling, since in preliminary studies, it was observed that vertigo (incidence ≥5%) may be an AE likely related to FNC;
- Monitoring drug interactions and AEs on a daily basis;
- Monitoring symptoms, vital signs, oximetry and blood glucose daily;
- Collection of blood samples and respiratory sample (nasal and oropharyngeal swab) for safety and efficacy monitoring tests every 48h);
- CT scan of the lung every 4 days and electrocardiogram on days D1 and D11;

The Principal Investigator may adjust the procedures performed during treatment according to the condition of the research participant and the results of clinical examinations.

VISIT 17: END OF TREATMENT (D15)

At the end of treatment or discontinuation of the investigational drug or PLACEBO, all participants will be required to undergo procedures and tests for safety and efficacy monitoring. The procedures should be performed before discharge from the hospital approximately 24 hours after the administration of the last dose of the investigational drug or PLACEBO, because for the 5 mg dose of AZVUDINE, the mean half- life is 13.8 hours, and it is excreted in the urine within 24 hours.

The treatment will last up to 14 days, and may be stopped early in case of

treatment success (2 consecutive negative RT-PCR tests), participant dropout, or at the Principal Investigator's option, if deemed necessary for the safety of the participant.

The following procedures will be performed at the V17 visit:

- Monitoring drug interactions and AEs;
- Symptom monitoring, vital signs, oxygen and blood glucose measurement;
- Collection of blood samples and respiratory sample (nasal and oropharyngeal
- swab) for safety and efficacy monitoring tests;
- CT scan of the lung and electrocardiogram.
- Collecting blood for a pregnancy test (women of childbearing age).

VISIT 18: FOLLOW-UP (D21)

Participants who, even after the end of treatment, remain in the hospital must undergo the procedures and tests for safety and efficacy monitoring that are scheduled to occur approximately 7 days after the administration of the last dose of the investigational drug or PLACEBO.

The following procedures will be performed at the V18 visit:

- Monitoring drug interactions and AEs;
- Symptom monitoring, vital signs, oxygen and blood glucose measurement;
- Collection of blood samples and respiratory sample (nasal and oropharyngeal
- swab) for safety and efficacy monitoring tests;
- CT scan of the lung and electrocardiogram;

Participants who are not discharged from the hospital after the end of treatment will be required to follow the follow-up schedule on D28 and D60. However, safety procedures and examinations will not be exclusive to these days and research participants who still remain hospitalized will be assisted at all times by the Principal

Investigator and his team.

VISIT 19: FOLLOW-UP (D28)

Two weeks after discharge from the hospital, the volunteers will return to the research center for procedures and tests to monitor safety and efficacy after the end of treatment.

The following procedures will be performed at the V19 visit:

- Symptom monitoring, vital signs, oxygen and blood glucose measurement;
- CT scan of the lung and electrocardiogram.

The Principal Investigator may adjust the procedures performed during the hospital visit according to the condition of the research participant and the results of the clinical examinations.

VISIT 20: FOLLOW-UP (D60)

60 days after discharge from the hospital, the volunteers will return to the research center to undergo procedures and tests to monitor safety and efficacy.

The following procedures will be performed in visit V20:

- Symptom monitoring, vital signs, oxygen and blood glucose measurement.
- Collecting blood for a pregnancy test (women of childbearing age).

The Principal Investigator may order tests according to the participants' previous results.

IGZ-1

AZVUDINE Clinical Trial Design

Schedule of visits and procedures

Week/Day	D-1	D0	D1	D2	D3	D4	D5	D6	D7	D8	D9	D10	D11	D12	D13	D14	D15 after the start of treatment	D21 ⁵ after the start of treatment	D28 after start of treatment	D60 after the start of treatment ³
Visit	1	2	3	4	5	6	7	8	9	10	11	12	13	14	15	16	17	18	19	20
Interval of the visit	± 4 days	-	-	-	-	-	-	-	-	-	-	1	1	1	-	-	Antes da alta hospitalar	± 3 dias	± 3 dias	± 3 dias
STAGES	TREAT	RANDOMIZATION							BLINDI	ED TRE	ATMEN	NT¹					END OF TREATMENT ²		FOLLOW-UP	
TCLE	Х																			
DEMOGRAPHIC INFORMATION	Х																			
ANAMNESIS	Х																			
ELIGIBILITY CRITERIA	Х																			
RANDOMIZATION		X																		
DISPENSING OF THE MEDICATION		Х																		
MEDICATION ACCOUNTING		X																		
SYMPTOM MONITORING	Х					•	•			Χ		•	•	•	•	•	X	X	Х	X
VITAL SIGNS	Х		X									Χ	Χ	X	X					
FINGER OXYGEN PULSE	Х		X									Х	X	Х	Х					
BLOOD GLUCOSE			X										Х	X	Х	Х				
PREGNANCY EXAM ⁴	Х																X			X

IGZ-1

AZVUDINE Clinical Trial Design

CT LUNG		Х		Χ				Χ				Χ				X	X	X	
ECG		Χ										Χ				Χ	X	X	
RT-PCR	Х	Х		Χ		Χ		Χ		Χ		Χ		Χ		Χ	X	X	
BIOCHEMICAL EXAMINATIONS	Х	Х		Χ		Χ		Х		Χ		Χ		Х		Χ	X	Х	
T-LYMPHOCYTES		Χ		Χ		Χ		Χ		Χ		Χ		Χ		Χ	X	X	
СВС		Χ		Χ		Χ		Χ		Χ		Χ		Χ		Χ	X	X	
FUNCTION OF COAGULATION		Х														Χ	X	X	
ESR/VHS		Χ						Χ								Χ	X	X	
CARDIAC MARKERS AND ENZYMES		Х						Х								X	Х	Х	
C-REACTIVE PROTEIN		Χ						Χ								Χ	X	X	
PROCALCITONIN		Х						Х								Χ	X	Х	
IL-6		Χ						Χ								Χ	X	X	
PHOSPHORUS IN URINE		Χ														Χ	X	X	
IMMUNOLOGICAL MARKERS		Х															Х	Х	
INFECTIOUS DISEASES		Χ																	
RESPIRATORY PARASITES		Х																	
TRIPLE TEST FOR RESPIRATORY PARASITES		Х															Х	Х	
AZVUDINE OR PLACEBO ADMINISTRATION			X																

IGZ-1

AZVUDINE Clinical Trial Design

MONITORING DRUG INTERACTIONS		X	X		
AE MONITORING		X	X		

Tabela 10: Cronograma de visitas e procedimentos do estudo.

¹ Day 1 of administration will be recorded as day 1 (D1) and the treatment days follow until day 14 (D14). The Principal Investigator may adjust the procedures performed during treatment according to the condition of the research participant and the results of clinical examinations (the condition manifests itself more rapidly in some patients and these patients should be observed closely).

² The examinations and procedures under visit 17 (D15) must be performed by all participants as soon as the treatment is terminated, including participants who have stopped treatment early (AT) and for any other reason.

³ The. procedures and examinations planned to be performed at visit D28 and D60 will be determined by the Principal Investigator according to the participants' previous examinations.

⁴ For women of childbearing age only.

⁵ Visit 18 procedures will be performed only on research participants who are still hospitalized.

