5.2. STUDY POPULATION

5.2.1. Recruitment and Selection

The research center is responsible for defining the strategies for recruitment and initial screening of research participants, so the **recruitment strategy will be the healthcare network**, since patients with moderate to severe stage COVID-19 symptoms eventually seek hospital care.

The fundraising strategy foresees the attraction of volunteers, through agents of prospection, in the entire region of Norte Fluminense, in addition to patients who seek care locally. The recruitment also involves partnerships with the Health Secretariats of the North and Northwest Fluminense region and their municipalities, which do not have a robust infrastructure for hospital care.

Municipalities: Campos dos Goytacazes, Cardoso Moreira, São Fidélis, São Francisco de Itabapoana, São João da Barra, Carapebus, Conceição de Macabu, Macaé and Quissamã, from the northern fluminense; and Itaperuna, Bom Jesus do Itabapoana, Italva, Laje do Muriaé, Natividade, Porciúncula, Varre-Sai, Santo Antônio de Pádua, Aperibé, Cambuci, Itaocara, Miracema, and São José de Ubá, from the Fluminense northwest.

After screening with the nursing staff of the health units, axillary temperature,

blood pressure, pulse oximetry, heart rate, respiratory rate, and the presence of risk factors (such as age over 65 years, hypertension, diabetes, cardiovascular disease, cerebrovascular disease, lung disease, immunosuppression, cancer, or use of immunosuppressive medications) are checked. An assessment by the qSOFA *score* should also be performed to find out if the patient has had contact with someone with suspected or confirmed COVID-19 and if the patient works in a healthcare facility or provides patient care. The nursing team then classifies the management according to color: green (mild cases), yellow (moderate cases), or red (severe cases).

Yellow rating means that it is a moderate stage II disease (inflammatory stage). In this stage, the patient may present with persistent cough plus daily persistent fever or persistent cough plus progressive worsening of another symptom related to COVID-19 (adynamia, prostration, hyporexia, diarrhea, decreased general condition, significant myalgia, moderate dyspnea, with or without hypoxia) or at least one of the above symptoms plus the presence of a risk factor. At this stage, the management is hospital admission in a ward/apartment.

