If hospitalization is indicated, a rapid test for COVID-19 will be performed, and if the result is positive, the clinical study will be presented by the prospecting team and an invitation to participate in the study will be extended. The consent process will be conducted by the prospecting agents in the field, duly delegated and trained to conduct the process, as well as to apply the Informed Consent Form (ICF). Multimedia resources will be used to clarify and instruct the volunteer about the objectives and details of the study. At the end of all the necessary clarifications, the volunteer will be asked to sign the ICF, where one copy will remain with the volunteer and another will be destined to the research center.

If the patient accepts to be a study volunteer, he/she and his/her companion, if applicable, will be informed of the study procedures, including the laboratory tests for the screening period, the criteria for inclusion and exclusion from the study, his/her rights and duties, the period of treatment and follow-up. The eligibility criteria may be

explored after the anamnesis, laboratory tests, and imaging tests have been performed, but may also be suspended at any time prior to complete evaluation if exclusions are identified by the study team. After this phase, the participant will be invited to sign the ICF and, only after signing, the volunteer will be included in the study. Clinical and laboratory evaluations and collection of nasopharyngeal and oropharyngeal swab specimens for RT-PCR testing confirm the eligibility of the study participant and will be assessed once all screening values are available.

Research participants who meet the inclusion criteria and do not meet the exclusion criteria, and who have eligibility assessed by the Principal Investigator, will be eligible.

The volunteer will then be transferred to Santa Casa de Misericórdia de Campos, via the regulatory center for hospital admission in a ward/apartment, and will be immediately randomized to follow the Treatment Protocol for COVID-19 of Santa Casa de Misericórdia de Campos (ANNEX1), as listed below:

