5.2.4. Exclusion Criteria

Individuals with one or more of the following characteristics will not be eligible to participate in this study:

- Patients known or suspected to be sensitive to AZVUDINE or excipients (inactive ingredients: microcrystalline cellulose, lactose hydrate, polyvinylpyrrolidone K30, croscarmellose sodium, magnesium stearate);
- Patients diagnosed with pneumonia caused by other pathogens;
- Patients with liver disease (total bilirubin ≥2mg/dL, ALT/TGP and AST/TGO ≥5 times above normal limit); ¹⁰
- Total neutrophil count <750 cells/L;
- Patients with renal insufficiency (glomerular filtration rate ≤60mL/min/1.73m2) or are receiving continuous renal replacement therapy, hemodialysis, or peritoneal dialysis;
- Patients with congestive heart failure (NYHA grade 3/4), untreated symptomatic arrhythmias, or myocardial infarction within 6 months;

HRH.org 華 人 □

AZVUDINE Clinical Trial Design

- Patients with a history of known liver disease (cirrhosis with ChildPugh classification B and C);
- Individuals with malabsorption syndrome, or other conditions that affect gastrointestinal absorption, and circumstances in which patients need intravenous nutrition, or cannot take medications orally or nasogastrically;
- Women who are pregnant or lactating, or of childbearing potential during the study period and within 6 months after termination of administration;
- Patients already included in other clinical trials;
- Patient under treatment for HIV, Hepatitis C, active Hepatitis B;
- Patients being treated with other antivirals (e.g. lopinavir/ritronavir, remdesivir, umifenovir/arbidol, favipiravir, interferon-α);
- Patients being treated with monoclonal antibodies (e.g. tocilizumab and sarilumab/kevzara);
- Patients who are on a clinical treatment plan that includes concomitant
 administration of any other experimental treatment or off-label use of
 already marketed drugs (e.g. hydroxychloroguine sulfate);
- Patients requiring invasive mechanical ventilation or extracorporeal membrane oxygenation (ECMO) at the time of randomization;
- Any clinically significant medical condition or medical history that, in the investigator's opinion, may discourage participation in the study, such as corrected QT interval >480 on the electrocardiogram, among other conditions.

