11.2. STATISTICAL ANALYSIS POPULATION

- Full Analysis Set (FAS): a set of patients who were randomized and received at least one oral dose of the study drug.
- Per protocol set (PPS): a set of data generated by a subset of clinical trial subjects whose protocol compliance was strict, with no significant

deviation from the trial protocol, to ensure that the data are statistically relevant to answer the primary endpoint. PPS analysis will be used for the primary efficacy indicator.

 Safety data set (SS): a set of participants who have received at least one treatment, and have actual data recorded by the safety index after treatment. The SS analysis will be used for the incidence of adverse reactions.

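### Sections 5.2.1 and 7.3 contradict each other on whether randomisation comes before or after transfer to the trial hospital, and the 7.3 order allows avoidable loss of randomised participants before any dose

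*Protocol*

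**What the plan says.** **Order of events.** Protocol Section 7.3, Visit 2 (D0): "eligible individuals will be randomized to the experimental or control group and then transferred to Santa Casa". The Visit 2 procedure list keeps this order. After randomisation it names "Admission or transfer of the participant to the apartment or infirmary of Santa Casa de Misericórdia de Campos", followed by dispensing. Protocol Section 5.2.1 has the volunteer "transferred to Santa Casa de Misericórdia de Campos, via the regulatory center for hospital admission in a ward/apartment, and will be immediately randomized".

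**Where participants come from.** Section 5.2.1 recruits "through agents of prospection, in the entire region of Norte Fluminense, in addition to patients who seek care locally". It names 9 northern and 13 north-western municipalities, 22 in all, including the trial hospital's own city. Section 5.1.4 names one trial hospital. Visit 1 accepts patients already in hospital and patients for whom admission is indicated.

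**Start of treatment.** Randomisation is D0. Section 7.3 then states: "The treatment period will start on D1 according to randomization". Table 10 counts D1 as the first day of administration, and Sections 6.2.4 and 7.3 set administration at 8 pm.

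**Rules that act between randomisation and the first dose.** Section 5.2.4 excludes "Patients requiring invasive mechanical ventilation or extracorporeal membrane oxygenation (ECMO) at the time of randomization". Section 9.4 stops study drug when intubation is needed, because the drug is oral. Section 6.2.4 gives study drug only while the participant is in hospital. Section 11.2 defines the full analysis set (FAS) as "a set of patients who were randomized and received at least one oral dose of the study drug" and uses the per-protocol set for the primary efficacy indicator.

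**The concern.** Staff who follow different sections would randomise at different points in the admission pathway. Under 7.3, allocation is fixed while a participant recruited elsewhere has still to be moved and admitted, and eligibility on ventilation status is settled before that move. The protocol asks for no second check on arrival.

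Participants lost in that interval have been randomised but have had no dose, so they drop out of the FAS, the widest efficacy set defined. At stake is post-randomisation exclusion that a different order would partly avoid. It departs from analysing everyone as randomised and uses up places in a trial of 180. A FAS limited to dosed participants is easiest to defend in a blinded trial when dosing follows closely on randomisation, and the 7.3 order weakens that defence.

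**Working it through.** **1. The two orders side by side**

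| Step | Section 5.2.1 | Section 7.3, Visit 2 |
|---|---|---|
| Consent and screening | before both | before both |
| Transfer/admission to trial hospital | before randomisation | after randomisation |
| Randomisation | immediately after transfer | before transfer |
| Ventilation/ECMO exclusion (tested at randomisation) | on arrival | before transfer |

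**2. How a randomised participant leaves the FAS under 7.3**

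- Not admitted: no study drug is given outside hospital (6.2.4), so no dose and not in the FAS.
- Intubated before the first dose: 9.4 stops the oral drug. Applied before a first dose, which is a natural reading although 9.4 is written for drug already started, this again means no dose and not in the FAS.

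**3. Time available for this.** No interval in hours is stated. If D1 is the calendar day after D0 and dosing is at 20:00, randomisation at the very start of D0 leaves 24 + 20 = 44 hours, and at the very end of D0 leaves 20 hours. These are outer bounds from the day numbering, and they apply under either order.

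**4. The plan's own sample size.** Inputs from Section 11.1: p1 = 0.667, p2 = 0.281, delta = 0.386, margin = 0.205, alpha = 0.05, beta = 0.2, 1:1.

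n per arm = (z_alpha + z_beta)² × [p1(1 − p1) + p2(1 − p2)] / (delta − margin)²

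- Variance term: 0.667 × 0.333 + 0.281 × 0.719 = 0.2221 + 0.2020 = 0.4242
- With one-sided alpha: (1.645 + 0.842)² = 6.183
- n = 6.183 × 0.4242 / 0.181² = 80.04, rounded up to 81 per arm, or 162
- With 10% dropout: 162 / 0.9 = 180

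The stated figures are reproduced with a one-sided 0.05. Section 11.3 declares two-sided tests; that is a separate matter and does not affect this point.

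**5. Effect of pre-dose loss on power.** The documents give no rate, so a range is assumed, with the loss taken on top of the full 10% dropout:

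n left per arm = 90 × (1 − loss) × 0.9

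power = Φ(0.181 / √(0.4242 / n) − 1.645)

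| Assumed loss before first dose | Of 180 | Left per arm | Power | Total needed to keep 162 |
|---|---|---|---|---|
| 0% | 0 | 81.0 | 80.4% | 180 |
| 2% | about 4 | 79.4 | 79.7% | 184 |
| 5% | 9 | 77.0 | 78.6% | 190 |
| 10% | 18 | 72.9 | 76.7% | 200 |

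**The case against.** - **Place of allocation.** A reader might infer from 7.3 that participants are allocated at a referring unit. No section says so. Section 5.4.1 randomises through the trial software with the principal investigator's agreement, and Visit 2 groups validation, randomisation, admission or transfer, and dispensing in one D0 visit. The Visit 2 item covers admission as well as transfer, so a participant already at the trial hospital has no transfer to fail. This stands. What remains is that 7.3 puts allocation before admission for those who do have to be moved.
- **Who is lost.** A reader might infer that the gap removes the sickest patients. Severe cases are eligible, so early intubation is possible, but no rate of deterioration or failed transfer is given, and both sections describe admission to a ward or apartment. The frequency is unknown.
- **Bias between arms.** The trial is double-blind with a matching placebo, so loss before dosing should be largely unrelated to arm. The documents do not support a claim that the treatment contrast is biased.
- **Dropout allowance.** Section 11.1 defines drop-outs broadly enough to cover some of these losses, so adding them on top of the 10% is the less favourable assumption. Even then the power effect is small.
- **Reach of the remedy.** Changing the order does not close the wait from D0 to 8 pm on D1. Nor does it settle the separate questions of a dosed-only FAS and a per-protocol primary analysis.

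None of this removes the contradiction. The Visit 2 list repeats the order in the 7.3 text, so loose wording in one sentence does not explain it.

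**Conclusion.** The contradiction is real and must be reconciled. Following 7.3 can lose randomised participants before any dose, and the FAS definition then excludes them. This rests on the texts of 5.2.1, 7.3, 5.2.4, 9.4 and 11.2, and on reading 9.4 as barring a first dose after intubation.

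The size of the loss cannot be derived from the documents. Over an assumed 2% to 10%, power by the protocol's own formula is 79.7% to 76.7%, against 80.4% with no such loss. The case for change is therefore a clear, single procedure and fewer avoidable exclusions after randomisation. It does not rest on a demonstrated bias or a material loss of power.

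**What to change.** Use the order of Section 5.2.1 in the Visit 2 text and procedure list of Section 7.3:

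1. consent and screening;
2. transfer and admission to the trial hospital;
3. confirmation there that the existing ventilation/ECMO exclusion is still not met;
4. randomisation, within the 96-hour PCR window of Sections 5.2.3 and 7.5.

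Table 10 has no transfer row, so it holds no conflicting order to correct.

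The cost is an amendment to the wording and a short eligibility check on arrival. A few transferred patients may prove not randomisable, or may pass the 96-hour window, after taking up a bed. Those losses fall before randomisation and so do not touch the randomised comparison.

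The sponsor should also reconcile the timing of randomisation with the existing administration schedule, since the D0-to-D1 interval remains under either order. Moving randomisation and the first dose to the same day would alter the D0 and D1 columns of Table 10. No change to dosing time or day is proposed here.

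### The neutrophil and QTc exclusions have no test scheduled before randomisation, and the neutrophil limit is printed in a unit that excludes essentially nobody

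*Protocol*

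**What the plan says.** **Order of events.** Section 7.3, Visit 2 (D0), reads: "After confirmation of eligibility for the study by meeting the inclusion and exclusion criteria and performing the screening procedures, eligible individuals will be randomized". Treatment starts on D1 (section 7.3, Visits 3-16).

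**Screening tests.** The Visit 1 list has a general item, "Collect blood and respiratory samples (nasal and oropharyngeal swabs) for screening tests", plus history, vital signs and a pregnancy test. It names neither an ECG nor a blood count. The Visit 2 list contains no test at all.

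**Purpose of the tests.** The opening of section 7 states that the tabulated tests serve eligibility assessment as well as safety and efficacy monitoring. (It cites Table 39; the list is Table 9.) That list includes the ECG and a CBC with neutrophils.

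**First scheduled occurrence.** Section 7.3, Visits 3-16: "CT scan of the lung every 4 days and electrocardiogram on days D1 and D11". In Table 10 the RT-PCR and biochemistry rows carry a D-1 mark. The ECG and CBC rows do not.

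**Exclusions that use these tests.** Section 5.2.4 excludes on "Total neutrophil count <750 cells/L". It also gives "corrected QT interval >480 on the electrocardiogram" as an example of a condition that may lead the investigator to exclude a patient. The synopsis repeats both.

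**The concern.** An exclusion criterion works only if its test result exists when the decision to randomise is made. Here one numeric laboratory exclusion and one named ECG exclusion have no scheduled pre-randomisation measurement. The authors did place the biochemistry behind the liver and renal exclusions at D-1, so the gap looks like an oversight.

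The neutrophil criterion has a second fault: its printed limit cannot select anyone. This matters because section 2.3 names the haematopoietic immune system as a target organ at the high dose in dogs, and section 8.3 lists decreased neutrophils among events possibly related to the product.

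The analysis is also exposed. Section 11.2 assigns the primary efficacy indicator to the per-protocol set, which admits only participants without significant deviations. Section 10.8 counts unmet eligibility criteria as a deviation. Ineligibility discovered on D1 can therefore remove a randomised participant from the primary comparison.

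**Working it through.** **1. Reading Table 10.** The lower part of the table came through with 19 cells per row against 20 day columns (D-1, D0, D1 to D14, D15, D21, D28, D60), so the alignment has to be checked. Two readings are possible:

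| Row | If the D0 column was lost | If cells are read from the left with no loss |
|---|---|---|
| RT-PCR | D-1, D1, D3, D5, D7, D9, D11, D13, D15, D21, D28 | D-1, D0, D2, D4, D6, D8, D10, D12, D14, D15, D21 |
| ECG | D1, D11, D15, D21, D28 | D0, D10, D14, D15, D21 |
| CBC | D1, D3, D5, D7, D9, D11, D13, D15, D21, D28 | D0, D2, D4, D6, D8, D10, D12, D14, D15, D21 |

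The text supports the first reading. Section 5.1.1 gives respiratory and blood sampling on D1, D3, D5, D7, D9, D11 and D13, and section 7.3 gives the ECG on D1 and D11. The second reading contradicts both.

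The finding does not depend on this choice. Under either reading the D-1 cell is blank for ECG and CBC and filled for RT-PCR and biochemistry. Even if the first marks were on D0, the Visit 2 list contains no test.

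**2. The sequence for the two criteria.**

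| Criterion (5.2.4) | Test needed (Table 9) | Named at Visit 1 or D-1? | First scheduled | Randomisation |
|---|---|---|---|---|
| Neutrophil count | CBC | No | D1 | D0 |
| QTc | ECG | No | D1 | D0 |

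**3. The neutrophil unit.** 1 L = 1,000,000 microlitres.

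- As printed: 750 / 1,000,000 = 0.00075 cells per microlitre, or 0.75 cells per millilitre.
- The same number per microlitre would be 750 × 1,000,000 = 750,000,000 cells per litre, a factor of one million.

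That the printed limit excludes essentially nobody rests on one assumption from ordinary laboratory practice: blood neutrophils are counted per microlitre, and a patient with fewer than one per millilitre is not a realistic case. A lost micro sign in the PDF cannot be fully ruled out. However, the sign survives elsewhere in the document (for example in sections 5.1.3 and 5.3.2), and the same wording stands in both eligibility lists.

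**4. What follows on D1.** Dosing is at 8 pm. If a disqualifying D1 result is ignored or arrives late, the participant is dosed against a safety exclusion and can then leave the per-protocol set for the deviation. If the result arrives in time and no dose is ever given, the participant also leaves the full analysis set, which requires at least one dose (section 11.2). In each case the loss comes after randomisation.

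**The case against.** The strongest reply is that the protocol does place laboratory work before eligibility in general terms. Visit 1 collects blood for screening, sections 5.1.1 and 5.2.1 have laboratory results evaluated before eligibility is decided, section 5.2.1 adds imaging, and eligibility waits until the screening data are complete. A site might well run a blood count at that point. This stands as far as it goes. A reader might infer that all 180 participants are randomised without these results, and the documents do not show that. They show that no list or table requires the two tests in time.

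A reader might also infer that every test-based exclusion fails, because serology and the respiratory-pathogen panel likewise have no D-1 mark. The text does not support that. The infection criterion is worded "Patient under treatment for HIV, Hepatitis C, active Hepatitis B", so treated cases can be found from the history and medication record taken at Visit 1. The other-pathogen criterion concerns pneumonia that has already been diagnosed. Neither needs a screening assay to be applied.

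Three further points limit the concern:

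- QTc is an example inside an investigator-judgement clause, not a stand-alone rule.
- With evening dosing, D1 results could arrive before the first dose. That may prevent dosing, but the participant is already randomised.
- Table 10 is a damaged extraction. The drug administration row is laid out differently and would start on D2 if the D0 column were dropped there too. The D1 date for CBC is therefore inferred from the anchored rows; the blank D-1 cell is not.

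Finally, a laboratory would probably not apply the printed neutrophil limit literally. That makes the error easy to notice but leaves the actual limit unstated.

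**Conclusion.** The point holds for the blood count and the ECG. The schedule contradicts the requirement to confirm exclusions before D0, and the neutrophil limit has no effect as printed. The first conclusion rests on the Visit 1 and Visit 2 lists, the stated ECG days and the blank D-1 cells. The second rests on the unit conversion and the assumption about ordinary neutrophil counts.

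The number of participants affected cannot be given: the protocol states no rate of neutrophil or QTc failure, and any count would be invented. This is a fault to correct in the amendment because it concerns safety exclusions and can remove randomised participants from the primary analysis set. It does not show that the eligibility criteria as a whole are unworkable.

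**What to change.** Reconcile section 5.2.4, the opening of section 7, the visit lists in section 7.3 and Table 10. Name the blood count and the ECG at Visit 1 and mark them at D-1, with results required before randomisation on D0. The sponsor should state the intended neutrophil unit in both the synopsis and section 5.2.4.

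Both tests are already planned, and section 7.5 allows up to 4 days between screening and randomisation. There are two costs. Some tests will be spent on patients who then fail screening. Some may also have to be done at referring units: Visit 2 in section 7.3 puts transfer to the study hospital after randomisation, whereas section 5.2.1 describes transfer first. That order should be settled in the same revision, because it decides where the tests are done.
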